6.1.2 Disposition

Disposition will be described for the following study phase:

- Screening,
- Treatment,
- Safety follow-up (for those subjects who do not enter LTE)

and include numbers of subjects completing each study phase and reasons for non-completion.

The following will also be summarized:

- Subject validity and validity exclusion reasons,
- the number of subjects enrolled, assigned to study treatment, completing the main study, completing the safety follow-up and entering the LTE.

Summaries will be presented overall (all ages), by age group and by concomitant PAH medications.

Subject will be defined as main study completer, if he/she has completed the week 24 treatment period.

6.1.3 Demography

Demographic data includes age at screening (years), sex, race and smoking among others. This data will be listed and summarized in tables. Summaries will be presented overall (all ages), by age group and concomitant PAH medications for SAF set and will be repeated for subjects who discontinued treatment.

The above presentation will be part of the DMC package.

6.1.4 Baseline characteristics

The following baseline characteristics are observed at baseline. In case of repeated measures the last available value before the first application of the study drug will be used for summary tables.

Primary diagnosis of Pulmonary Hypertension (PH)-IIP, 6MWD, WHO functional class, BNP/NT-proBNP, SF10, PedsQL, bone age and morphology and tanner scale.

Primary diagnosis of Pulmonary Hypertension (PH)-IIP information presented in the corresponding listing will be part of the DMC package.

6.1.5 Medical history

Medical history will be evaluated by a frequency table, showing number of subjects with medical history findings coded according to the Medical Dictionary for Regulatory Activities (MedDRA), last available version at the time of database lock, and analyzed by system organ class (SOC) and preferred term (PT).

6.1.6 Prior and concomitant medication

Prior and concomitant medication will be listed and summarized in frequency tables. Medications will be coded according to the World Health Organization Drug Dictionary Enhanced (WHO-DDE), last available version at the time of database lock. For this study, separate outputs will be generated for previous and concomitant PAH specific medication and other (non PAH specific) medication.

Missing or incomplete start and stop dates of medication will be imputed as described in section 4.3 about Missing Data.

The medications will be classified as follows:

- Medications that began before the start of study drug (regardless of when they ended) are defined as ‘medication before start of study drug’.
- Medications that started and stopped before the start of study drug are defined as ‘medication that started and ended before administration of study drug’.
- Medications that are ongoing at, began after the start of study drug, or medications that were started after end of study drug are defined as ‘concomitant medication’.
- Medications that began after the start of study drug, and those that were started after end of study drug are defined as ‘new concomitant medication’.

Medications will be tabulated overall (all ages), by age group and concomitant PAH medications for SAF.

SDG/BDG will be used to select concomitant medications of special interest: PAH specific medication, Background therapy/supportive PH therapy and Safety relevant medication. The selected concomitant medications will be summarized by parent SDG/BDG, SDG/BDG and substance name. The information will be provided separately and will be part of the analysis datasets specifications. Summaries will be done for all selected concomitant medications, new selected concomitant medications, and selected medications taken before start of study drug.

6.1.7 Study medication duration and exposure

Study medication can be administered as tablets or as oral suspension formulation of 0.15 mg/mL. For the analysis the equivalent dose (mg) will be used. The derivation rule is:

- For tablets: No conversion needed. The dose (mg) is identical to the equivalent dose (mg).
- For oral suspension: The volume of suspension (ml) will be converted into equivalent dose (mg) as described in the protocol [Table 5–2](#): Body weight-adjusted riociguat dosing schedule, considering the weight at that timepoint.

Treatment duration and exposure will be analyzed for the SAF set and presented overall (all ages), by age group and concomitant PAH medications. The cumulative treatment exposure will be analyzed for the SAF set and presented overall (all ages), by age group and concomitant PAH medications by suitable treatment exposure intervals.

Duration of treatment is defined as the number of weeks from start of treatment until the last day the study drug administration in respective phase divided by 7 (i.e. $[\text{end date} - \text{start date} + 1] / 7$). Duration of treatment will be summarized by study phase descriptively and by suitable time intervals using frequency counts. Dose titration by visit, dose titration sequence

and reasons for up- and down-titration by visit and dose will also be summarized using frequency counts.

Extent of exposure will be summarized descriptively and by suitable dosing intervals using frequency counts.

Cumulative treatment duration will be summarized by total person years, excluding subjects with missing duration, and uses 365.25 days per year in the calculation. Cumulative treatment duration will include individual titration phase and maintenance phase.

Extent of exposure in mg will be calculated as follow:

- Tablets: sum of all doses [mg] within a time interval
- Oral suspension: sum of all drug amount [ml] within a time interval multiplied with 0.15 mg/mL. The dose will be in mg.

The overall extent of exposure is the sum of all extent of exposures of a patient.

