**Table 5–2 : Body weight-adjusted riociguat dosing schedule**

Body weight (kg)	0.5 mg equivalent TID (mg)/	equivalent volume of suspension TID (mL)*	1.0 mg equivalent TID (mg)	equivalent volume of suspension TID (mL)*	1.5 mg equivalent TID (mg)	equivalent volume of suspension TID (mL)*	2.0 mg equivalent TID (mg)	equivalent volume of suspension TID (mL)*	2.5 mg equivalent TID (mg)	equivalent volume of suspension TID (mL)*
≥12<14	0.12	1.0	0.25	1.75	0.37	2.50	0.50	3.25	0.62	4.25
≥14 <16	0.14	1.0	0.28	1.75	0.42	2.75	0.56	3.75	0.70	4.75
≥16 <18	0.15	1.0	0.31	2.00	0.46	3.00	0.62	4.25	0.77	5.00
≥18 <20	0.17	1.0	0.33	2.25	0.50	3.25	0.67	4.50	0.83	5.50
≥20 <25	0.19	1.25	0.38	2.50	0.57	3.75	0.75	5.00	0.94	6.50
≥25 <30	0.22	1.50	0.44	3.00	0.66	4.25	0.87	6.00	1.09	7.50
≥30 <35	0.25	1.75	0.50	3.25	0.74	5.00	0.99	6.50	1.24	8.50
≥35 <40	0.28	1.75	0.56	3.75	0.84	5.50	1.12	7.50	1.41	9.50
≥40 <50	0.33	2.25	0.66	4.50	1.00	6.50	1.33	9.00	1.66	11.00
≥ 50	0.50	3.25	1.00	6.50	1.50	10.00	2.00**	13.50	2.50**	16.50

Abbreviations: TID = three times daily

\* For facilitation of administration of a proper body-adjusted dose, the volumes of suspension are provided with increments of 0.25 mL (for 1-5 mL) and 0.5 ml (for over 5 ml)

\*\* For change in weight category from 40-<50 kg to ≥ 50 kg, IXRS will administer intermediate dose to adjust to 0.5 mg increment (e.g. intermediate dose for 2.0 mg equivalent is 1.50 mg /10.00 mL; for 2.5 mg equivalent is 2.00 mg / 13.50 mL).

*(Note: The table was modified according to Amendment 3, see Section 17.1.1.6.)*

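### SAP 6.1.7 announces equivalent mg but computes extent of exposure for suspension in actual mg, so the summary varies with body weight at the same nominal dose regimen

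*SAP*

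**What the plan says.** SAP 6.1.7 contains two rules for turning study drug into mg.

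The opening rule is general: "For the analysis the equivalent dose (mg) will be used". Tablets need no conversion. For suspension, "The volume of suspension (ml) will be converted into equivalent dose (mg) as described in the protocol", with a reference to Table 5-2 ("Body weight-adjusted riociguat dosing schedule") and to the child's weight at the time.

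The later rule applies to extent of exposure. For tablets: "Tablets: sum of all doses [mg] within a time interval". For suspension: "Oral suspension: sum of all drug amount [ml] within a time interval multiplied with 0.15 mg/mL". The patient total then combines everything: "The overall extent of exposure is the sum of all extent of exposures of a patient".

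On presentation, the section says: "Treatment duration and exposure will be analyzed for the SAF set and presented overall (all ages), by age group and concomitant PAH medications". Neither formulation nor weight band is a stratum. Extent of exposure is also to be counted in dosing intervals. Nothing in the section says that extent of exposure is an exception to the opening rule.

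Under Protocol 5.4, children below 50 kg at baseline take suspension three times a day during the 24-week phase, and children of 50 kg or more take tablets.

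**The concern.** Volume times 0.15 mg/mL gives the mass of riociguat swallowed. It does not give the adult-equivalent dose that the opening rule asks for. For tablets the two quantities coincide; for suspension they do not, because Table 5-2 gives lighter children fewer mg for the same equivalent level. Putting both on one mg scale mixes two quantities under one label.

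The regimen is weight-adjusted precisely so that children reach an exposure similar to that of treated adults (Protocol 5.1.1). A total in actual mg undoes that adjustment. In the overall and age-cohort summaries, lighter and typically younger children would appear less exposed even when they followed the same equivalent-dose steps as the tablet patients. Two programmers could also read the section differently and produce different tables.

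**Working it through.** **Inputs.** Volumes and mg per equivalent level come from Protocol Table 5-2. The suspension strength is 0.15 mg/mL (Protocol 5.4, SAP 6.1.7). Dosing is three times a day for 24 weeks, so 168 days × 3 = 504 doses. The start level is 1.0 mg equivalent, with steps of 0.5 mg every two weeks up to 2.5 mg (Protocol 5.1.1).

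**Step 1: reproduce Table 5-2.** Volume × 0.15 against the tabulated mg at the 2.5 mg equivalent level:
- 40 to <50 kg: 11.00 × 0.15 = 1.65 (table 1.66)
- 20 to <25 kg: 6.50 × 0.15 = 0.975 (table 0.94)
- 12 to <14 kg: 4.25 × 0.15 = 0.6375 (table 0.62)

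All 50 cells of the table agree to within one pipette increment. The extent-of-exposure formula therefore returns the actual mg column, not the equivalent level.

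**Step 2: ratio per dose.** Equivalent mg ÷ (volume × 0.15), range over the five dose levels:

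| Weight | Ratio |
|---|---|
| 12 to <14 kg | 3.33 to 4.10 |
| 14 to <16 kg | 3.33 to 3.81 |
| 16 to <18 kg | 3.14 to 3.33 |
| 18 to <20 kg | 2.96 to 3.33 |
| 20 to <25 kg | 2.56 to 2.67 |
| 25 to <30 kg | 2.22 to 2.35 |
| 30 to <35 kg | 1.90 to 2.05 |
| 35 to <40 kg | 1.75 to 1.90 |
| 40 to <50 kg | 1.48 to 1.54 |
| ≥50 kg, tablets | 1.00 |

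The maximum is 2.0 / (3.25 × 0.15) = 2.0 / 0.4875 = 4.10.

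**Step 3: 24-week total for full up-titration.** Assume 1.0, 1.5 and 2.0 mg equivalent for 14 days each (42 doses each), then 2.5 mg equivalent for 126 days (378 doses), with every dose taken and weight staying in one band.

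- Tablets: 42 × (1.0 + 1.5 + 2.0) + 378 × 2.5 = 189 + 945 = 1134 mg
- 40 to <50 kg: [42 × (4.50 + 6.50 + 9.00) + 378 × 11.00] × 0.15 = 4998 mL × 0.15 = 749.7 mg; 1134 / 749.7 = 1.51
- 20 to <25 kg: [42 × (2.50 + 3.75 + 5.00) + 378 × 6.50] × 0.15 = 2929.5 mL × 0.15 = 439.4 mg; ratio 2.58
- 12 to <14 kg: [42 × (1.75 + 2.50 + 3.25) + 378 × 4.25] × 0.15 = 1921.5 mL × 0.15 = 288.2 mg; ratio 3.93

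Under the opening rule of 6.1.7, each of these children would total 1134 mg.

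**The case against.** The strongest reply is that the later rule is a deliberate, specific definition. It has its own formula and says that the result is in mg, and drug mass is a legitimate quantity. On that reading the equivalent dose governs the dose-level tables and actual mg governs extent of exposure. This may be what was intended, but the section does not say so. It declares one metric for the analysis, uses another, and calls both mg. Even on this reading the table needs a label and a stated exception.

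Three further points limit the consequence, and all stand. Mixing formulations within one child should be uncommon in the main phase (Protocol 5.4 foresees it if weight falls below 50 kg), so the issue lies in summaries across children. The documents give no weight distribution, and both age cohorts can include children under 50 kg, so the size of the effect on the age-cohort table cannot be calculated. The results are descriptive, and no test or sample size depends on them.

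A reader might infer that younger children would also look under-titrated. The documents do not support that. SAP 6.1.7 separately tabulates titration by visit, titration sequence and reasons for dose changes, and under the opening rule those tables show equivalent levels.

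A reader might also infer that the primary safety results are distorted. SAP 6.4.1 presents adverse events by dose group (0.5 to 2.5 mg three times a day) and overall, and no planned rate is divided by cumulative mg. Treatment duration is in weeks and person-years, which weight does not change.

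**Conclusion.** The point holds as an unlabelled change of metric within SAP 6.1.7. It affects only the descriptive extent-of-exposure summaries and their dosing-interval counts.

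The roughly fourfold gap is an extreme. It belongs to the 12 to <14 kg band, which Amendment 12 added because such children may be enrolled; the documents do not say how many are expected. Without that band the largest single-dose ratio is 3.81.

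The totals rest on the full up-titration schedule, complete intake and a stable weight band. The children compared share a nominal equivalent-dose regimen. Whether they share the same systemic exposure is a pharmacokinetic question that the trial itself is meant to answer, so it should not be assumed here.

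**What to change.** In SAP 6.1.7, define extent of exposure for all children as the sum of equivalent dose in mg, using the Table 5-2 conversion that the section already states. The recorded assigned equivalent level would serve equally well if it is available in the analysis data. Protocol 5.1 shows the interactive response system allocating the dose, but the documents do not show that those levels reach the analysis datasets.

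If actual mg is also wanted, report it as a separate, clearly labelled quantity, by formulation or per kg body weight.

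The cost is one SAP sentence and one derived variable. No new data collection is needed for the Table 5-2 route, because it uses the volumes and weights that the section already relies on.

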6.2 Efficacy

6.2.1 Primary efficacy

Please refer to section 6.3.

6.2.2 Secondary efficacy

Efficacy is evaluated in exploratory manner based on SAF and assessed as change from baseline to end of treatment (week 24). All data except PedsQL data are part of the DMC package.

It includes following endpoints:

- **6-Minute Walking Distance (6MWD)**

6MWD will be analyzed descriptively by summary tables. Time points of efficacy assessments are at baseline and week 24.

- **WHO functional class**

WHO functional class will be analyzed descriptively using frequency tables. Time points of efficacy assessments are at baseline and week 24.

- **Laboratory biomarker (NT-proBNP or BNP)**

NT-proBNP or BNP will be analyzed descriptively by summary tables. Time points of efficacy assessments are at baseline and week 24.

- **Child Health-related Questionnaire (SF-10)**

SF-10 scores (Physical Summary Score, and Psychosocial Summary Score) will be analyzed descriptively by summary tables. Time points of efficacy assessments are at screening and week 24.

- **Generic Core Scales self-report (PedsQL)**

Summary scores of all three types of questionnaires (Young Child Report (age: 5-7), Child Report (age: 8-12), Teen Report (age: 13-18)) will be analyzed overall (all age groups together) and by age cohort (≥ 6 to < 12 years and ≥ 12 to < 18 years) by summary tables. Time points of efficacy assessments are at screening and week 24.

Following Summary Scores will be analyzed:

- Physical Functioning Dimension
- Emotional Functioning Dimension
- Social Functioning Dimension
- School Functioning Dimension
- Physical Health Summary Score (equal to Physical Functioning Dimension)
- Psychosocial Health Summary Score
- Total Score

• **Echocardiography**

There are following echocardiography parameters assessed:

Table 6–1: Echocardiography parameters

General description (in clinical study protocol)	Parameters in data
Pulmonary arterial systolic pressure (PASP)	Pulmonary artery systolic pressure
Tricuspid annular plane systolic excursion (TAPSE)	Tricuspid annular plane systol. Excursion
Pericardial effusion	Finding for pericardial effusion
	Pericardial effusion
Left ventricular eccentricity index	Left ventricular eccentricity index
Right atrial pressure	Estimate of mean right atrial pressure
Right ventricular pressure by tricuspid regurgitant jet velocity	Tricuspid regurgitation peak velocity
Acceleration time of pulmonary flow	Pulmonary artery acceleration time
Right heart dimensions (i.e. Right atrial and Right ventricular)	Right atrial diastolic area index
	Right atrial systolic area index
	Right atrial diastolic area
	Right atrial systolic area
	Right ventricular diastolic area
	Right ventricular systolic area
	Right ventricular diastolic area index
	Right ventricular systolic area index
Cardiac output	Right Ventricular Cardiac Output
	Right Ventricular Cardiac Index

Assessments by Central Reader will be listed and analyzed descriptively by sample summary statistics. Time points of assessments are at baseline and week 24. Investigator’s assessments (Echocardiography Local) will be listed only.

Supplementary parameters (Diameter, vena cava inferior, baseline; Minimum inferior vena cava diameter; Left Ventricle-Short axis perpendicular; Left Ventricle-Short axis parallel; Pressure gradient of tricuspid valve; Respiratory collapsibility, v. cava inf.; right ventricular outflow tract – velocity time intergral; Right ventricular stroke volume; Heart Rate; Right

Ventricular Outflow Tract Area; Right Ventricular Outflow Tract Diameter) used to derive echocardiography parameters (Table 6–1) will be listed only.

• **Time to clinical worsening (TTCW):**

Time to clinical worsening is defined by the first of any of the following events:

- Hospitalization for right heart failure
(Preferred term (PT) as described in Table 6–2 AND requires or prolongs hospitalization = ‘Y’)
- Death (all cause mortality)
(all deaths during both treatment and follow-up period)
- Lung transplantation
(PT = ‘Lung transplant’)
- Pott’s anastomosis and/or atrioseptostomy
(Subject has either PT = ‘Systemic-pulmonary artery shunt’ OR PT = ‘Balloon atrial septostomy’ or both. The first event occurred will be considered.)
- Increase in WHO FC from baseline
- Appearance/worsening symptoms of right heart failure and need for additional PAH therapy (PT as described in Table 6–2 AND therapy as described in Table 6–3 at same day or up to 6 days before or after.)

Table 6–2: Right heart failure

Preferred Term (at least one must apply)
Acute right ventricular failure
Chronic right ventricular failure
Right ventricular failure
Pulmonary arterial hypertension

Table 6–3: Need for additional PAH therapy

Drug class	Compound (at least one must apply)
Endothelin receptor antagonist	Ambrisentan
	Bosentan
	Macitentan
Phosphodiesterase-5 inhibitor	Sildenafil
	Tadalafil
	Udenafil
Prostacyclin analogue	Beraprost
	Epoprostenol
	Iloprost
	Treprostinil
Prostacyclin agonist	Selexipag

TTCW will be analyzed descriptively by sample summary statistics.

All Kaplan-Meier estimates will be summarized.

In addition, Kaplan-Meier plots will be generated for the TTCW. Subjects without signs of worsening at the time of the main study or LTE phase analysis will be right censored at the date of end of main phase or the date of subject's study termination, whatever occurs first.

For subjects with event: Time to clinical worsening (weeks) = integer[(date of first event – treatment start date + 1) / 7].

For subjects without event: Time to worsening (weeks) = integer[(date study termination/ end of main phase – treatment start date +1) /7]. Date of study termination is defined as date of last visit. Date end of main phase is defined as date of the last visit of the main phase (Visit 9 for subjects continuing in LTE phase or safety follow-up visit for subjects not continuing in LTE phase).

TTCW will be part of the DMC package.

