## 4. Study population

### 4.1 Planned number of subjects - amended

Children on treatment with ERAs and/or PCAs can be enrolled. At least 20 children on treatment with bosentan or other Endothelin Receptor Antagonists (ERA) must be enrolled in the study.

The sponsor commits to put efforts in enrolling equal number of subjects in each of the  $\geq 12$  to  $< 18$  year and the  $\geq 6$  to  $< 12$  year age cohort overall. Enrolment will be started with children from 12 to less than 18 years of age.

After 5 patients in the  $\geq 12$  to  $< 18$  years old group have reached their optimal dose, have been treated on their maintenance dose and obtained the control x-ray of left hand at week 24, their data will be evaluated by DMC. Only after obtaining positive safety and efficacy data in the first 5 patients, enrolment in the group from 6 to less than 12 years of age will be started.

The sponsor will make every effort to facilitate an equal distribution between the two age cohorts with a minimum of 5 patients in each age cohort. In case of inadequate availability of patients in the age group  $\geq 6$  to  $< 12$  years total enrolment will be stopped only if at least 5 patients of this younger age group have been enrolled.

*(Note: The Section was modified according to Amendment 6, see Section 17.3.1.2. The Section was modified according to Amendment 9, see Section 17.4.1.9)*

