## **6.3 Efficacy/Pharmacodynamic/Other outcomes - amended**

Main secondary endpoints will be assessed as:

Change from baseline to end of treatment (week 24) of:

- 6-Minute Walking Distance (6MWD)
- WHO functional class
- Lab N-terminal prohormone brain-type natriuretic peptide or brain-type natriuretic peptide (when both tests are available, NT-proBNP should be chosen over BNP and the same test should be performed at every required visit)
- Quality of Life scores (parent questionnaire and in children able to understand questions): Child Health-related Questionnaire (SF-10) and PedsQL Generic Core scales self-report
- Echocardiographic parameters including pulmonary arterial systolic pressure (PASP), right ventricular pressure by tricuspid regurgitant jet velocity, tricuspid annular plane systolic excursion (TAPSE), pericardial effusion, left ventricular eccentricity index, estimated right atrial pressure, acceleration time of the pulmonary flow, right heart dimensions, and computing of cardiac output.

Time to clinical worsening

- Hospitalization for right heart failure
- Death
- Lung transplantation
- Pott's anastomosis and atrioseptostomy
- Worsening of PAH symptoms, which must include either:
  - an increase in WHO FC
  - OR*
  - appearance/worsening symptoms of right heart failure
  - AND*
  - need for additional PAH therapy.

Other endpoints assessed in the study will be:

- Taste and texture of the pediatric formulation(s) must be assessed by use of a questionnaire at the beginning and at the end of treatment (week 24).
- Right heart catheterization

A change in RHC parameters (if available) obtained from RHC performed before study enrollment and during study conduct.

*(Note: The paragraph was modified according to Amendment 5, see Sections 17.2.1.2, 17.2.1.3 and 17.2.1.7. The Section was modified according to Amendment 6, see Sections 17.3.1.2, 17.3.1.3, and 17.3.1.6. This section was modified according to Amendment 9, see Sections 17.4.1.7 and 17.4.1.13.)*

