## **7.5 Determination of sample size - amended**

Children on treatment with ERAs and/or PCAs can be enrolled. At least 20 subjects on treatment with bosentan or other Endothelin Receptor Antagonists (ERA) must be enrolled in the study. The sample size does not originate from a formal sample size calculation, but is based on an evidence-based feasibility assessment. Based on the results of the evidence-based feasibility survey (Davie, 2014) and the proposed PK evaluation (see section 7.4.3), 20 patients will permit an accurate PK evaluation and feasibility of the study in a reasonable time frame. Every effort will be made to enroll equal numbers of patients in both age cohorts (see section 4.1).

*(Note: The Section was modified according to Amendment 6, see Section 17.3.1.2. This section was modified according to Amendment 9, see Section 17.4.1.13.)*

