4.1 General Principles

The statistical evaluation will be performed by using the software package Statistical Analysis Software (SAS) release 9.4 or higher (SAS Institute Inc., Cary, NC, USA). All variables will be analyzed by descriptive statistical methods.

1. The number of data available and missing data, mean, standard deviation (SD), minimum, 25% and 75% quartiles, median, and maximum will be calculated for metric data. Mean, median, quartiles and SD will be reported to one decimal place greater than the data were collected. Minimum and maximum values will be reported with the same precision as they were collected. The same metrics will be calculated for the change in parameters between Baseline and visits after Baseline.
2. Frequency tables will be generated for categorical data. These include the counts and percentages of each category including the category 'missing' as a separate category, if applicable. Percentages will be calculated using a denominator of all subjects in the specified population, and the percentage values will be reported to one decimal place. If an incidence is $< 0.1\%$ but $> 0\%$, it will be displayed as " $<0.1\%$ ".
3. If no data exists for a table, an empty table will be provided. The text in that table should read "No data matched the selected criteria".
4. For tables that fit horizontally on a single page, and that are more than one page in length, "Continued" will be added to the bottom of all but the last page. The word "Continued" must be added to the title for all pages after the first page and to the bottom of the page for all pages from the first to the second to last page.
5. For event-based tables the number of subjects should be displayed next to the treatment with the syntax "(N=x)". For tables where the N is the number of subjects and also used as the denominator "N=x (100%)" is to be used.
6. In frequency tables, if "n=0", then only "0" should be displayed; "(0.0%)" will not be displayed.
7. When numerator and denominator values are "0", do not use brackets. Use the following: "0/0", not "0/0 (%)".
8. All listings will be presented for subjects with their subject identifier, age at screening, sex and race.

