6.4.7 Physical examination and growth chart

Subject's overall development is assessed by physical examination, growth chart (height and weight) evaluation and pubertal development using Tanner scale, see protocol section 18.3, and at the discretion of the investigator in case of clinical suspicion for bone and/or growth anomalies. Pubertal assessment using Tanner scale will be performed every 12 months. Abnormal physical examination findings are recorded as medical history, if they started before providing written informed consent/assent. If the abnormal finding started or deteriorated after providing written informed consent/assent, it is documented as adverse event.

Height, weight, BMI will be summarized by visit and will be presented overall (all ages), excluding subjects with down-syndrome. BMI will be presented for non-Asian, i.e. excluding Japanese and Taiwanese, population only.

In addition a frequency table of growth parameter percentiles by visit and by age group and concomitant PAH medications will be presented for height, weight and BMI. Subjects with down-syndrome will be excluded. The percentiles are based on CDC growth standards [6] and growth chart for Japan for Japanese and Taiwanese subjects provided by sponsor [7].

For the calculation of percentiles, age in months at each visit will be calculated. Due to the fact, that only year of birth is collected the calculation of age in months will be:

$(\text{year of visit} - \text{year of birth}) * 12$

Pubertal assessment using Tanner scale will be summarized as shift table for change from baseline by visit.

Growth parameters by visit and Tanner scale listing are part of the DMC review.

7. Document history and changes in the planned statistical analysis

- SAP final version 1.0, dated 12 OCT 2015
- SAP final version 2.0, dated 15 JAN 2016. SAP was updated to reflect protocol changes and is based on protocol version 2, Amendment 3, from 24 NOV 2015.
- SAP final version 3.0, dated 24 AUG 2016. SAP was updated to reflect protocol changes and is based on protocol version 3, Global Amendment 5, from 31 MAY 2016 and stand-alone Amendment 4, from 08 MAR 2016. Further updates were done to reflect the changes of the DMC Charter and is based on the DMC Charter version 3.0, from 01 JUN 2016.

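### WHO functional class is defined as a change, but no table of children improved, unchanged or worsened is named; growth has no age-standardised within-child change, and the calendar-year age rule distorts percentile shifts.

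*SAP*

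**What the plan says.** **Functional class.** Protocol 6.3 lists WHO functional class under the stem "Change from baseline to end of treatment (week 24) of". SAP 6.2.2 opens by saying that efficacy is assessed as that change. The analysis line then reads "WHO functional class will be analyzed descriptively using frequency tables", followed by the two time points. Protocol 7.4.2 likewise gives frequency tables for categorical efficacy parameters.

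**General rules.** SAP 4.1 states that "All variables will be analyzed by descriptive statistical methods". Item 1 extends the summary statistics to change from baseline for metric data. Item 2 gives categorical data counts and percentages per category and does not mention change.

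**Growth.** SAP 6.4.7 summarises height, weight and BMI by visit over all ages. It adds "a frequency table of growth parameter percentiles by visit and by age group" and concomitant PAH medication. Percentile bands are not stated. Age for the percentiles is year of visit minus year of birth, times 12, because only the birth year is collected. The same section says "Pubertal assessment using Tanner scale will be summarized as shift table for change from baseline by visit". No shift table is named for functional class or for growth percentiles.

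**Size.** Protocol 7.5: "At least 20 subjects on treatment with bosentan or other Endothelin Receptor Antagonists (ERA) must be enrolled in the study" and "The sample size does not originate from a formal sample size calculation". Protocol 4.1 aims at equal age cohorts "with a minimum of 5 patients in each age cohort".

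**The concern.** In a single-arm study of about 20 children, the within-child comparison is the main information on response. If functional class is reported as one distribution at baseline and another at week 24, the reader sees the net movement but not how many children moved each way. A drug that helps two children and harms none can give the same two tables as one that helps ten and harms eight.

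Growth is a safety question that the protocol itself raises: section 1.2 describes growth-plate findings in growing rats, and section 8.8 makes bone and growth anomalies an event of special interest. Raw height rises with normal growth and is pooled over ages 6 to 17. A table of percentile bands absorbs most small shifts. The age rule adds a further problem. Between two visits 24 weeks apart, a child's computed age either stands still or jumps a full year, so the percentile moves even when growth is normal.

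**Working it through.** The plan states no power, alpha or precision figure for these outputs, so there is none to reproduce.

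**1. What two marginal tables determine (functional class)**

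Illustrative margins, N = 20, classes I/II/III: baseline 2/12/6, week 24 4/10/6. I enumerated all 3 × 3 tables with these margins.

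- Fewest movers: two children go from II to I and nobody else moves. That is 2 improved, 0 worsened.
- Most movers: 4 go from II to I, 6 from III to II, 2 from I to II, 6 from II to III, and 2 stay in II. That is 10 improved, 8 worsened.
- Check on the second case: class I = 4; class II = 6 + 2 + 2 = 10; class III = 6.

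If the number worsened were known from another output, the range would narrow but usually not close:

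| Worsened | Improved, possible range |
|---|---|
| 0 | 2 |
| 2 | 2 to 6 |
| 4 | 3 to 8 |
| 8 | 6 to 10 |

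A shift table gives the counts exactly. With N = 20, exact 95% intervals would be 0% to 16.8% for 0 children and 5.7% to 43.7% for 4 children.

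**2. What the percentile table can register (growth)**

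Assumptions: bands at 5, 10, 25, 50, 75, 90 and 95, and standard normal z-scores. The share of children crossing a band after a fall of d is the sum over boundaries b of Φ(b + d) − Φ(b).

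- d = 0.1: 0.159, about 3 of 20 children
- d = 0.2: 0.318, about 6 of 20

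For scale, assume growth of 5 cm/year and a height SD of 6 cm. Growth over 24 weeks is 5 × 168/365.25 = 2.30 cm. A 25% slowdown is 0.25 × 2.30/6 = 0.10 SD. Over 4 to 7 cm/year and an SD of 5 to 7 cm, it is 0.07 to 0.16 SD.

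**3. The age rule**

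If visits fall evenly over the year, the chance that a 24-week interval crosses 1 January is 168/365.25 = 0.46. Computed age therefore advances 12 months in about 46% of children and 0 months in about 54%. The true interval is 5.5 months. For a child growing normally (5 cm/year, SD 6 cm), the false z-shift is:

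- same calendar year: +2.30/6 = +0.38
- new calendar year: (2.30 − 5)/6 = −0.45

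Over 4 to 7 cm/year and an SD of 5 to 7 cm, the false shifts run from +0.26 to +0.64 and from −0.31 to −0.76. Each is several times the 25% slowdown under the same assumptions. The SD of this artefact at 5 cm/year and SD 6 cm is (5/6) × √(0.46 × 0.54) = 0.42.

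**4. Precision of a paired z-change, N = 20**

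The 95% half-width is t(19) × SD/√20, with t = 2.093. The SD of true z-change is assumed.

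| Assumed SD | Age rule corrected | Age rule as in the SAP |
|---|---|---|
| 0.1 | 0.05 | 2.093 × √(0.1² + 0.42²)/√20 = 0.20 |
| 0.2 | 0.09 | 2.093 × √(0.2² + 0.42²)/√20 = 0.22 |

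With 5 children in a cohort, the corrected half-widths are 0.12 and 0.25.

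**The case against.** **A shift table may already be planned.** A reader might infer that functional class will appear only as two separate tables. The SAP does not say so. The words by visit attach to the growth percentiles, the opening sentence of 6.2.2 covers functional class as a change, and layouts are deferred to company standards and table shells outside the documents. This stands as a limit on the claim. It is also a reason to name the table, as was done for Tanner stage.

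**Worsening is counted elsewhere.** An increase in functional class from baseline is an event in time to clinical worsening (SAP 6.2.2), and zero events would settle the example at exactly 2 improved. This stands in part. The endpoint is a first-event composite, no component counts are specified, and a class increase after another event is not counted. Improvement is not covered.

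**Within-child growth is not absent.** SAP 4.1 yields change from baseline in raw height, weight and BMI. That is correct, but these changes are not age-standardised. Bone age and morphology are read centrally, the DMC evaluates the hand X-rays, and growth velocity is monitored in the extension, which has its own SAP. One should therefore not infer that growth harm would go unmonitored.

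**A paired z-score is no cure by itself.** This stands: under the present age rule it would mostly measure whether the new year fell between visits. Nor could a single arm attribute a precise change to the drug.

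**Conclusion.** The gap is real and modest: a free improvement to an exploratory, descriptive analysis. For functional class, the endpoint is a change and no output named in the SAP gives the numbers improved, unchanged and worsened. The range from 2/0 to 10/8 depends on illustrative margins and on having the two marginal tables alone. The documents do not support saying that within-child change cannot be seen at all, since worsening enters the composite.

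For growth, no age-standardised within-child change is specified, and the age rule can move a normally growing child by roughly +0.4 or −0.45 z over 24 weeks. That affects the planned percentile table as well as any z-score added to it. The sizes rest on assumed growth rates, height SD, percentile bands, SD of z-change and an even spread of visits over the year; the documents give none of these. The 0.05 to 0.09 half-width is attainable only after the age rule is changed.

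**What to change.** 1. **SAP 6.2.2.** Add a baseline-by-week-24 shift table for WHO functional class, with counts improved, unchanged and worsened. Exact confidence intervals are optional. State that the existing rule assigning class IV after death applies in this table.
2. **SAP 6.4.7, age.** Fix one baseline age per child and add the actual elapsed time to each visit. Use a finer age where local rules permit. A fixed baseline age may still be wrong in level, but the error is then the same at every visit and largely cancels from the change.
3. **SAP 6.4.7, growth.** Add paired change from baseline in height-for-age and weight-for-age z-score (mean, SD, 95% CI), overall and by age cohort, on the reference charts already chosen. Keep the present exclusion of children with Down syndrome. Confirm that the chart used for Japanese and Taiwanese children supports z-scores. Keep the percentile table, state its bands, and compute it with the revised age.

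The cost is SAP wording, one changed derivation and the added tables. Nothing new needs to be collected, unless a finer age is sought.
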